## **7.2. Recording of Adverse Events**

Whenever possible, a unifying diagnosis should be recorded in the eCRF as the adverse event rather than individual signs or symptoms. Similarly, the unifying diagnosis should be recorded as the adverse event rather than the abnormal laboratory result (i.e., "anemia" instead of "low hemoglobin").

If the adverse event is a worsening of a past medical condition, the adverse event should clearly indicate that the past medical condition has worsened using words such as "worsening," "aggravated," or "exacerbation."

### **7.2.1. Recording of Non-Serious Adverse Events**

Collection of adverse events will begin immediately following signing of the ICF through the final study visit. The Investigator will monitor each subject closely and record all observed or volunteered adverse events. Adverse findings detected at the Screening visit (e.g., abnormalities on clinical laboratory testing, ECGs, physical/neurological examination) will be recorded on the Medical History CRF and adverse events occurring after the Screening visit but before starting study treatment will be recorded on the adverse event CRF and considered non-treatment emergent.

### **7.2.2. Recording of Serious Adverse Events**

Collection of serious adverse events will begin immediately following signing of the ICF through the final study visit. The Investigator will monitor each subject closely and record all observed or volunteered serious adverse events. Serious adverse events occurring after signing

the ICF but before starting study treatment will be considered non-treatment emergent. If a new serious adverse event comes to the attention of the Investigator after the completion of the final study visit, information regarding the serious adverse event should be collected and reported to the Sponsor only if assessed as reasonably possibly related to the study drug(s) by the Investigator.

After the initial serious adverse event report, the Investigator is required to proactively follow each subject and provide further information to the Sponsor (or designee) on the subject's condition. The Investigator will ensure that follow-up includes any supplemental investigations as may be indicated to elucidate the nature and/or causality of the serious adverse event. This may include additional laboratory tests or investigations, histopathological examinations, or consultation with other health care professionals.

Serious adverse events that remain ongoing past the subject's last protocol-specified follow-up visit will be evaluated by the Investigator and Sponsor. All serious adverse events will be followed:

- Until resolution, or
- For 28 days after the subject's last follow-up visit, or
- If, in the investigator's opinion, the condition is unlikely to resolve, whichever comes first. If the Investigator and Sponsor agree the subject's condition is unlikely to resolve, the Investigator and Sponsor will determine the follow-up requirement.

*Subjects experiencing a serious adverse event should have a single blood sample collected as soon as possible after the serious adverse event and within 48 hours for the pharmacokinetics of  $\alpha$ - and  $\beta$ -HTBZ, if possible. The date and time of the last dose of study drug should be recorded along with the date and time of the sample collection.*

### **7.3. Evaluation of Adverse Events (Serious and Non-Serious)**

At each in-person visit and telephone contacts, occurrence of adverse events will be assessed by verbally asking subjects and caregivers if they have had any problems or symptoms since their last visit.

If the subject or caregiver reports an adverse event, the investigator/coordinator will probe further to determine:

- Time of onset and resolution
- Frequency
- Causality/relation to study treatment
- Intensity
- Action taken regarding study drug
- Outcome

#### **7.3.1. Severity**

The Investigator will make an assessment of intensity for each adverse event and serious adverse event reported during the study. The assessment will be based on the Investigator's clinical judgment. The intensity of each adverse event and serious adverse event recorded in the eCRF should be assigned to one of the following categories:

- **Mild: Causes minimal discomfort, but does not interfere with normal daily activities**
- **Moderate: Causes sufficient discomfort to interfere with normal daily activities**
- **Severe: Prevents normal daily activities**

An adverse event that is assessed as severe should not be confused with a serious adverse event.

Severity is a category utilized for rating the intensity of an event; and both adverse events and serious adverse events can be assessed as severe. An event is defined as serious when it meets one of the pre-defined outcomes as described in Section 7.1.5.

### 7.3.2. Relationship to Study Drug

The Investigator is obligated to assess the relationship between study drug and the occurrence of each adverse event. The Investigator will use clinical judgment to determine if there is a reasonable possibility that the drug caused the adverse event. The investigator's assessment of the relationship of each adverse event to study drug will be recorded in the source documents and the eCRF. Alternative causes, such as medical history, concomitant therapy, other risk factors, and the temporal relationship of the event to the study drug should be considered and investigated, if appropriate. The Medical Monitor's opinion may be sought in those cases in which the Site Investigator is unable to make an independent judgment. The Medical Monitor may in turn consult with the Principal Investigator as needed. The following definitions are general guidelines only to help assign grade of attribution:

- **Unrelated:** The adverse event is **clearly not related** to the investigational drug
- **Unlikely:** The adverse event is **doubtfully related** to the investigational drug
- **Possible:** The adverse event **may be related** to the investigational drug
- **Probable:** The adverse event is **likely related** to the investigational drug
- **Definite:** The adverse event is **clearly related** to the investigational drug

### 7.3.3. Action Taken with Study Treatment

Action taken as a result of an adverse event will be recorded on the adverse event eCRF as follows:

- No change
- Dose reduced
- Drug suspended (see Section 5.2.4 for guidance in contacting Medical Monitor)
- Drug permanently discontinued

### 7.3.4. Treatment Required

Treatment required as a result of an adverse event will be recorded in the subject's source documents, and if medication is required, on the concomitant medications log:

- None
- Medication Required (record on Concomitant Medications eCRF)
- Hospitalization Required
- Other (specify)

If a diagnosis has been entered as an adverse event, the treatment(s) recorded may represent the treatment(s) given for one or more sign(s) or symptoms(s) (e.g., Naproxen for the adverse event "fracture", without recording "pain due to fracture" or "inflammation due to fracture" as separate adverse events).

### 7.3.5. Outcome

Outcome of an adverse event will be recorded on the adverse event eCRF as follows:

- Recovered / Resolved
- Recovering / Resolving
- Recovered / Resolved with Sequelae

- Not Recovered / Not Resolving
- Fatal
- Unknown

#### **7.4. Procedures for Reporting Serious Adverse Events**

All serious adverse events occurring during study participation must be reported to the Sponsor (or designee) and to the governing IRB/IEC as required by the IRB/IEC, local regulations, and the governing health authorities.

##### **7.4.1. Completion and Transmission of the Serious Adverse Event Report**

Once an Investigator becomes aware that a serious adverse event has occurred in a study subject, she/he will report the information to the Sponsor (or designee) within 24 hours. The serious adverse event form (provided in the study Operations Manual) will always be completed as thoroughly as possible with all available details of the event, signed by the Investigator (or designee), and forwarded to the Sponsor (or designee) within the designated time frames. If the Investigator does not have all information regarding a serious adverse event, he/she will not wait to receive additional information before notifying the Sponsor (or designee) of the event and completing the form. The form will be updated when additional information is received. Whenever possible, the Investigator will provide an assessment of causality at the time of the initial report as described above.

The Sponsor will provide a list of project contacts for serious adverse event receipt. Any event that in the opinion of the Investigator may be of immediate or potential concern for the subject's health or well-being will be reported to the Sponsor (or designee).

##### **7.4.2. Regulatory Reporting Requirements for Serious Adverse Events**

The Investigator must promptly (within 24 hours of awareness) report all serious adverse events to the Sponsor (or designee) in accordance with the procedures describe above. Prompt notification of serious adverse events by the Investigator to the appropriate project contact for serious adverse event receipt is essential so that legal obligations and ethical responsibilities towards the safety of other subjects are met. The Investigator will be responsible for reporting serious adverse events to the IRB/IEC per local regulatory requirements.

The Sponsor (or designee) is responsible for reporting serious adverse events to the relevant regulatory authorities in accordance with local regulations. That is, serious adverse events which are determined by the Sponsor to be "Unexpected" and classified as "Suspected Adverse Reactions" will be reported in an expedited manner.

#### **7.5. Procedures for Reporting Pregnancy Exposure and Birth Events**

The Investigator must promptly report all pregnancies in female study subjects to the Sponsor (or designee) in accordance with the Operations Manual. While the pregnancy itself is not considered to be an adverse event or serious adverse event, any pregnancy complications should be recorded as adverse events or serious adverse events. Any pregnancy will be followed through its conclusion for observation of any serious adverse events including congenital anomalies/birth defects.

## 8. STATISTICAL PROCEDURES AND DATA ANALYSIS

This section describes the statistical analysis strategy and procedures for the study. Summary statistics will be provided by prior treatment (in parent study) and for the overall population. Descriptive statistics will be calculated for quantitative data and frequency counts and percentages will be provided for categorical data. Details of the data analysis will be described in a separate Statistical Analysis Plan.

### 8.1. Analysis Populations

**Safety Population:** The Safety Population will include all subjects who were administered any study drug. Subjects who are assigned a subject number but withdrew prior to dosing will not be included in the Safety Population. If relevant, details of their participation and reason for withdrawal will be listed separately in the study report.

All summaries of safety endpoints in will be summarized descriptively in the Safety Population.

**Intent-to-Treat (ITT) Population:** The ITT Population will include all enrolled subjects in the study. All efficacy measures in Part A will be summarized using the ITT Population.

**Randomized Withdrawal ITT Population:** The Randomized Withdrawal ITT Population will include all subjects enrolled to Part B of the study.

**Randomized Withdrawal Modified Intent-to-Treat (mITT) Population:** The Randomized Withdrawal mITT Population will include all subjects enrolled to Part B who receive study drug during the Randomized Withdrawal Period and have a centrally read AIMS score at both the Pre-withdrawal Visit and the Post-withdrawal Visit. All efficacy measures in the Randomized Withdrawal Period will be analyzed using the Randomized Withdrawal mITT Population.

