#### **3.2. Safety Population**

The Safety population will include all patients who were administered any study drug. Patients who were enrolled but withdrew prior to dosing will not be included in the safety population.

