#### **3.3. Randomized Withdrawal ITT Population**

The randomized withdrawal ITT population will include all patients enrolled in Part B of the study.

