#### **3.4. Randomized Withdrawal Modified Intent-to Treat Population**

The randomized withdrawal modified intent-to-treat (mITT) population will include all patients enrolled in Part B who receive study drug during the Randomized Withdrawal Period and have a total motor AIMS score as assessed by blinded central video rating at both the Pre-Withdrawal Visit and the Post-Withdrawal Visit.

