## **7.2. Part B**

### **7.2.1. General**

The randomized withdrawal ITT population will be used for all Part B safety summaries. Summaries will be presented by randomized withdrawal treatment group (SD-809 and placebo) and overall for Part B visits.

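### SAP 7.2.1 summarises Part B safety in everyone enrolled in Part B, with no requirement that blinded drug was taken and no rule for grouping by treatment received

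*Protocol*

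**What the plan says.** Protocol 8.1 assigns safety to one study-wide set: "All summaries of safety endpoints in will be summarized descriptively in the Safety Population". Words seem to be missing before the verb. The set is defined in the same section: "The Safety Population will include all subjects who were administered any study drug". SAP 3.2 repeats that definition. Protocol 8.4 lists safety endpoints for Part B as well as Part A.

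For Part B the SAP names a different set. Section 7.2.1 states: "The randomized withdrawal ITT population will be used for all Part B safety summaries". On grouping it adds: "Summaries will be presented by randomized withdrawal treatment group (SD-809 and placebo) and overall for Part B visits". Section 3.3 defines the set: "The randomized withdrawal ITT population will include all patients enrolled in Part B of the study". No dosing condition appears in either place.

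A blinded-dose condition does appear in SAP 3.4. The mITT set, used for Part B efficacy, is limited to Part B patients "who receive study drug during the Randomized Withdrawal Period" who also have a central AIMS score at both visits.

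SAP Section 9, on changes to protocol-specified analyses, lists one item, which concerns ECG variables. The SAP Introduction says that the SAP takes precedence over the protocol and that differences will be explained in the study report.

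**The concern.** The withdrawal week is the study's only randomised, blinded comparison of SD-809 with placebo, and the tables in SAP 7.2 are its only safety read-out by randomised treatment. The combined Part A and B tables in SAP 7.1 also use these data, but group patients by parent-study treatment, so they give no SD-809 versus placebo contrast for that week.

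A safety table by treatment is normally read as describing people who took that treatment. Here the set does not guarantee it. The dosing condition sits in the efficacy set and is absent from the safety set, although a safety comparison has more need of it. The reader of the report also could not see how many patients were affected. SAP 5.1.2 counts ITT patients not treated for the study as a whole, but the Part B disposition table in 5.2.2 has no such row. It gives the ITT and mITT counts, and their difference mixes patients not dosed with patients lacking a central AIMS score.

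**Working it through.** **Which patients each set contains**

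| Set | Source | Condition | Part B patient who took no blinded drug |
|---|---|---|---|
| Safety Population | Protocol 8.1, SAP 3.2 | any study drug in the study | included |
| Randomized withdrawal ITT | SAP 3.3 | enrolled in Part B | included |
| Randomized withdrawal mITT | SAP 3.4 | blinded drug taken and both central AIMS scores | excluded |

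The first row follows from SAP 2.1: a patient must have been on a stable SD-809 dose for at least 4 weeks before Part B. Every eligible Part B patient has therefore already taken study drug. Replacing the ITT set with the Safety Population in SAP 7.2 would remove nobody. Neither document contains a set suited to the withdrawal-week safety tables.

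**Which tables are affected**

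SAP 4.4 bases by-visit summaries on observed data. An undosed patient with no Post-Withdrawal assessment adds nothing to the changes in laboratory values, vital signs, ECG or rating scales at that visit. The denominator question falls mainly on the adverse event table of SAP 7.2.3, which is descriptive.

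**Size**

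The plan gives no figure for this point. The only input taken from it is the 143 patients randomised 1:1 (SAP 2.3 and 2.4). I assume a split of 72 and 71. The documents give no count of undosed or mis-dispensed patients and no event rates for the withdrawal week, so the other inputs below are assumptions.

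1. *One patient with an event:* 1/72 = 1.4 percentage points of an arm.
2. *Undosed patients, 10 patients with events in an arm of 72:* the table shows 10/72 = 13.9%. With 3 undosed and event-free, the rate among dosed patients is 10/69 = 14.5%. With 5, it is 10/67 = 14.9%. The gaps are 0.6 and 1.0 points.
3. *General form:* if m of 72 are undosed and event-free, the rate shown is the rate among dosed patients × (72 − m)/72. A 20% rate is shown as 19.7% (m = 1), 19.4% (m = 2) or 18.9% (m = 4).
4. *Direction:* suppose the rates among dosed patients are 20% in one arm and 10% in the other, a difference of 10 points. Four undosed, event-free patients among 72 in the higher-rate arm give 18.9 − 10 = 8.9 points. Four in the lower-rate arm give 10 × 68/72 = 9.4%, so 20 − 9.4 = 10.6 points. The difference can shrink or grow.
5. *Wrong kit, if k patients in each arm received the other arm's kit and are tabulated as randomised:* with the same rates, the arm of 72 shows [(72 − k) × 20% + k × 10%]/72 and the arm of 71 shows [(71 − k) × 10% + k × 20%]/71. The difference falls from 10 points to 9.7 (k = 1), 9.4 (k = 2) or 8.9 (k = 4).

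**The case against.** The strongest objection is that no patient's inclusion changes between the two documents. A reader might infer that the SAP has left a dosed safety set for one that lets in undosed patients, and that returning to the protocol would put it right. The documents do not support that. The protocol's set is study-wide, and within Part B it holds the same eligible patients as the ITT set. The protocol sentence is also incomplete, so how it was meant to apply to Part B is not certain. This objection stands. The case for change rests on what a withdrawal-week safety table needs, not on restoring the protocol.

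Other inferences are also too strong:

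- *Mis-dispensed patients will be counted under the wrong drug.* SAP 7.2.1 does not say whether the group is as randomised or as received, and the protocol has no as-treated rule either. This is a gap in the plan, not a stated rule.
- *The plan expects undosed patients.* The dosing clause in the mITT definition allows for them without predicting any. Consent, randomisation and dispensing all belong to the Pre-withdrawal Visit (Protocol 6.4), so few are likely.
- *Undosed patients can only lower event rates, to the drug's advantage.* Protocol 6.9.8 and 7.2.1 record adverse events from consent onward regardless of causal relationship to the drug, so an undosed patient can have one. In a withdrawal design the placebo arm may also be the one with more events.

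It is also fair to say that no test is planned on these data, that no undosed or mis-dispensed patient is reported, and that the SAP already commits to explaining differences from the protocol in the study report. These points limit the importance of the issue. They do not supply the missing definition.

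**Conclusion.** The point holds in a limited form. SAP 7.2.1 uses a population with no blinded-dose condition and leaves the grouping rule unstated for the study's only randomised placebo comparison of safety. The protocol's Safety Population would not cure this. SAP Section 9 does not record that a different set is used.

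The consequence is small. It falls mainly on one descriptive adverse event table, at about 1.4 percentage points for each patient with an event in an arm of 72, and well under 2 points in the illustrations above. Those figures assume a 72/71 split, invented event rates and a handful of affected patients. The direction of any error cannot be fixed in advance. If all 143 patients were dosed as randomised, no Part B safety table changes. This is an inexpensive improvement to the plan; the material gives no ground to say that the Part B safety results are biased.

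**What to change.** - In SAP Section 3, define a Randomized Withdrawal Safety set: Part B patients who took at least one dose of blinded drug in the Randomized Withdrawal Period, grouped by the treatment actually received.
- Name that set in SAP 7.2.1 and use it through 7.2.7.
- Add to the Part B disposition table (SAP 5.2.2) the number randomised but not dosed with blinded drug, by arm.
- List the difference from Protocol 8.1 in SAP Section 9.
- Keep the randomized withdrawal ITT set for Part B disposition and baseline tables.

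The cost is one definition, one changed sentence, one table row and one entry in Section 9. No new data are needed. Protocol 6.4 already provides for randomisation through the interactive response system, drug collection and accountability at both withdrawal visits, and a pharmacokinetic sample at the Post-withdrawal Visit.

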### 8.2. Demographics and Baseline Data

Demographic information will be presented for each subject. Medical/surgical history data at baseline will be listed, as will physical examination data.

### 8.3. Safety Analyses

Safety and tolerability will be assessed throughout the study by monitoring the following parameters:

- Adverse events
- Clinical laboratory tests
- Physical examination
- Vital signs
- 12-lead ECGs
- UPDRS – Motor Examination
- BARS
- HADS
- C-SSRS
- ESS
- MoCA®

Safety data will be summarized descriptively for the overall population and based on prior treatment (SD-809 or placebo) in the parent study. Descriptive statistics will be calculated for quantitative data and frequency counts and percentages will be provided for categorical data. Descriptive statistics of change-from-baseline will use the Baseline from the present study (SD-809-C-20 Baseline).

The nature, frequency, and severity of adverse events will be tabulated for all subjects combined and by treatment. Baseline, within study, end of study, and change-from-baseline values for

clinical laboratory evaluations and vital signs will be summarized as appropriate. Treatment-emergent adverse events and laboratory, vital sign, and ECG parameters will be summarized. In addition, change from baseline will be summarized for laboratory and vital sign parameters. Shift tables will be provided for clinical laboratory results. ECG results will be classified as normal and abnormal and summarized.

#### **8.4. Safety Endpoints**

The following safety endpoints will be assessed in Part A:

- Incidence of adverse events, serious adverse events, severe adverse events, drug-related adverse events, adverse events leading to withdrawal during the following periods:
  - Overall
  - During titration
  - During long-term treatment
- Observed values and changes from baseline in clinical laboratory parameters (hematology, chemistry, and urinalysis)
- Observed values and changes from baseline in vital signs
- Observed values in ECG parameters and abnormal findings
- Number of subjects with on-treatment QTcF values >450 ms, >480 ms, >500 ms, or a change from Baseline in QTcF of >30 ms or >60 ms
- Observed values and changes in UPDRS Part III (motor examination), BARS, HADS, C-SSRS, ESS, and MoCA©
- Duration of time to achieve stable dosing of SD-809

The following secondary safety endpoints will be assessed in Part B:

- Incidence of adverse events, serious adverse events, severe adverse events, drug-related adverse events, and adverse events leading to withdrawal
- Observed values and changes from start of randomized withdrawal in clinical laboratory parameters (hematology, chemistry, and urinalysis)
- Observed values and changes from start of randomized withdrawal in vital signs
- Observed values in ECG parameters and abnormal findings
- Number of subjects with on-treatment QTcF values >450 ms, >480 ms, >500 ms, or a change from Baseline in QTcF of >30 ms or >60 ms
- Observed values and changes in UPDRS Part III (motor examination), BARS, HADS, C-SSRS, ESS, and MoCA©

The following secondary safety endpoints will be assessed in Part C:

- Secondary safety endpoints:
  - Incidence of adverse events, serious adverse events, severe adverse events, drug-related adverse events, and adverse events leading to withdrawal from start of Part C
  - Observed values and changes in vital signs from start of Part C
  - Observed values and changes in C-SSRS from start of Part C
  - Observed values in ECG parameters and abnormal findings from start of Part C

- Number of subjects with on-treatment QTcF values >450 ms, >480 ms, >500 ms, or a change from Baseline in QTcF of >30 ms or >60 ms from start of Part C

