### 7.1. Definitions

#### 7.1.1. Adverse Event

An adverse event is any untoward medical occurrence associated with the use of a drug in humans, whether or not considered drug related. An adverse event (also referred to as an adverse experience) therefore, can be any unfavorable and unintended sign (e.g., an abnormal laboratory finding), symptom, or disease temporally associated with the use of a drug, without any judgment about causality. An adverse event can arise from any use of the drug (e.g., off-label use, use in combination with another drug) and from any route of administration, formulation, or dose, including an overdose.

Examples of an adverse event include:

- Exacerbation of a chronic or intermittent pre-existing condition including either an increase in frequency and/or intensity of the condition.
- New conditions detected or diagnosed after study drug administration even though it may have been present prior to the start of the study.
- Abnormal safety assessments if they lead to study drug dose modification, study drug discontinuation or to therapeutic intervention (e.g., low hemoglobin that requires transfusions).
- Abnormal laboratory tests if they are associated with clinical signs, symptoms or if they lead to a diagnosis or therapeutic intervention.
- Abnormal vital signs if they are clinically significant and lead to a diagnosis or therapeutic intervention.
- Abnormal ECGs if they are clinically significant and lead to therapeutic intervention or diagnosis. The clinical significance should be confirmed by a cardiologist.
- Signs, symptoms, or the clinical sequelae of a suspected interaction.
- Signs, symptoms, or the clinical sequelae of a suspected overdose of either study drug product or a concurrent medication.

Examples of an adverse event do not include:

- A medical or surgical procedure (e.g., endoscopy); a condition that leads to the procedure is an adverse event.

- Situations where an untoward medical occurrence did not occur (social and/or convenience admission to hospital) or scheduled elective procedures like cosmetic surgery are not adverse events. However, if the procedure results in an unexpected complication, the complication is an adverse event.
- Anticipated day-to-day fluctuations of pre-existing disease(s) or condition(s) present or detected at the start of the study that do not worsen.

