## 8.5. Efficacy Measures

The following efficacy measures will be assessed during Part A:

- The change in AIMS score (items 1 through 7) from Baseline of this study at each visit that this is measured, as assessed by the site rating.
- The proportion of subjects who are a treatment success based on the CGIC at each visit that this is measured. A treatment success is defined as Much or Very Much Improved on the CGIC from Baseline of this study.
- The proportion of subjects who have a 50% or greater reduction in AIMS score from Baseline of this study at each visit that this is measured.
- The change in the modified CDQ-24 score from Baseline of this study at each visit that this is measured.
- The proportion of subjects who are a treatment success based on the PGIC at each visit that this is measured. A treatment success is defined as Much or Very Much Improved on the PGIC from Baseline of this study.
- The percent change in AIMS score from Baseline of this study at each visit that this is measured.

The following efficacy measure will be assessed during Part B (Randomized Withdrawal Period):

- Primary efficacy endpoint: change from Pre-withdrawal Visit AIMS scores (items 1 through 7) as assessed by blinded central video rating to the Post-withdrawal Visit between subjects treated with SD-809 and subjects treated with placebo.

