### **7.2.3. Adverse Events**

All AEs in the Part B Randomized Withdrawal Period will be summarized using descriptive statistics by system organ class and preferred term.

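### Part B adverse-event incidence by arm can include return of dyskinesia on placebo, which is also the efficacy outcome; tabulate it with and without TD-worsening terms

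*Protocol*

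**What the plan says.** **The endpoint.** Protocol section 8.4 lists for Part B "Incidence of adverse events, serious adverse events, severe adverse events, drug-related adverse events, and adverse events leading to withdrawal". SAP section 2.2.1 gives the corresponding list for the Randomized Withdrawal Period but leaves out severe events. SAP section 7.2.3 says: "All AEs in the Part B Randomized Withdrawal Period will be summarized using descriptive statistics by system organ class and preferred term". SAP section 7.2.1 adds: "Summaries will be presented by randomized withdrawal treatment group (SD-809 and placebo) and overall for Part B visits".

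**What counts as an adverse event.** Protocol section 7.1.1 gives as an example "Exacerbation of a chronic or intermittent pre-existing condition including either an increase in frequency and/or intensity of the condition". The related item among its non-events is "Anticipated day-to-day fluctuations of pre-existing disease(s) or condition(s) present or detected at the start of the study that do not worsen". Section 7.2 instructs sites: "If the adverse event is a worsening of a past medical condition, the adverse event should clearly indicate that the past medical condition has worsened". Under section 7.3, events are sought at every contact by "verbally asking subjects and caregivers if they have had any problems or symptoms since their last visit". Neither document exempts TD, lack of efficacy or an expected loss of effect.

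**The efficacy outcome.** The Part B primary endpoint in protocol section 8.5 is the change in AIMS items 1 to 7, "as assessed by blinded central video rating to the Post-withdrawal Visit between subjects treated with SD-809 and subjects treated with placebo".

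**The concern.** The same clinical event can enter the results twice. If SD-809 works, dyskinesia returns in the placebo arm during the blinded week. That is the contrast the AIMS endpoint is meant to detect. An investigator following sections 7.1.1 and 7.2 can also record it as a worsening of a pre-existing condition, and it then raises adverse-event incidence on placebo.

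This matters because the blinded week is the only randomized, placebo-controlled comparison of adverse events in the study. Part A is open-label and single-arm, and Part C continues SD-809. A reader of the Part B table could see a better profile on SD-809 that reflects efficacy, or could miss a modest excess of other events on SD-809.

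The overlap is hard to undo from the printed table. SAP section 7.1.3 counts a patient once per system organ class and once per preferred term (stated for the Part A tables). If Part B follows the same convention, subtracting a TD row from a class total or an any-event count goes wrong for every patient who has both kinds of event.

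**Working it through.** **1. The plan's own Part B figures.** No adverse-event rate is stated, so the only design figure to reproduce is the sample size, and this point does not rest on it. With difference 1.4, SD 2.9, two-sided 5% and 90% power:

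n per arm = 2 × (1.960 + 1.282)² × 2.9² / 1.4² = 90.2, rounded up to 91, as stated.

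The SAP reports 143 randomized, or 143 / 2 = 71.5 per arm. Power is then 82.3% (normal) or 81.8% (t-based), close to the approximately 80% stated.

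**2. Model for the any-event count.** Let b be the proportion with other adverse events, equal in both arms. Let wP and wA be the proportions with worsening of TD reported as an adverse event on placebo and SD-809, independent of other events. All of these are assumptions.

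- Any event on placebo = 1 − (1 − b)(1 − wP)
- Any event on SD-809 = 1 − (1 − b)(1 − wA)
- Spurious placebo excess = (1 − b)(wP − wA)

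| b | wP/wA = 0/0 | 5%/1% | 10%/2% | 20%/5% |
|---|---|---|---|---|
| 5% | 0 | 3.8 | 7.6 | 14.2 |
| 10% | 0 | 3.6 | 7.2 | 13.5 |
| 20% | 0 | 3.2 | 6.4 | 12.0 |

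Entries are percentage points. Example: with b = 10% and 10%/2%, placebo reads 1 − 0.90 × 0.90 = 19.0% (13.6 of 71.5 patients) and SD-809 reads 1 − 0.90 × 0.98 = 11.8% (8.4 patients), although other events are equally common.

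**3. Masking of a real difference.** Suppose other events truly occur in 15% on SD-809 and 10% on placebo, a 5-point excess. The apparent SD-809 minus placebo difference becomes:

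- 5%/1%: (1 − 0.85 × 0.99) − (1 − 0.90 × 0.95) = 15.85% − 14.5% = +1.35 points
- 10%/2%: 16.7% − 19.0% = −2.3 points
- 20%/5%: 19.25% − 28.0% = −8.75 points

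**4. Cross-check tied to the plan's effect size.** Suppose the change in dyskinesia is normal in both arms and is reported beyond a common threshold. The planned shift is 1.4 / 2.9 = 0.483 SD. Reporting of 10%, 20% and 30% on placebo then implies about 3.9%, 9.3% and 15.7% on SD-809. At b = 10% the excess is 0.90 × (10 − 3.9) = 5.5, 0.90 × (20 − 9.3) = 9.6 and 0.90 × (30 − 15.7) = 12.9 points, inside the range in step 2.

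**5. Effect of separating the terms.** With TD-worsening terms excluded, the spurious difference is zero in every scenario of step 2.

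**The case against.** The strongest reply is that loss of effect may never reach the adverse-event table. The non-event clause refers to conditions present at the start of the study, so dyskinesia that returns toward the untreated level, but not beyond it, can be read as not worse. The protocol also collects dyskinesia control separately from adverse events at both withdrawal visits (section 6.4 and the Part B schedule). This stands: reporting is at the investigator's discretion, and the effect may be zero. It does not remove the point, because nothing tells investigators to leave TD worsening out.

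The second reply is that the table is descriptive and untested, and that preferred-term rows show TD events apart from others. This also stands. Rows for other events are clean, and SAP section 7.1.3 plans listings of serious events and events causing discontinuation that can be inspected case by case. Only the aggregate counts are affected.

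Three stronger readings are tempting and are not supported:

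- A reader might infer a placebo excess of 9 to 27 points by taking 10% to 30% reporting on placebo and a 10% background (0.90 × 10 and 0.90 × 30). That sets reports of worsening on SD-809 to zero, which the documents give no reason to assume; steps 2 and 4 allow some.
- A reader might extend the point to severe events, since protocol section 8.4 names them. The SAP omits them from its Part B list, and its introduction says that the SAP prevails.
- A reader might infer that SD-809's safety record as a whole is flattered. The main safety tables combine Parts A and B by parent-study arm (SAP section 7.1.1), with no stated removal of the placebo week. There, TD worsening on placebo would count against SD-809.

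**Conclusion.** The point holds in limited form. The adverse-event definition can capture worsening of TD, no text exempts it, and Part B events are summarized by randomized arm. Where worsening is reported more often on placebo, the any-event, system-organ-class, drug-related and withdrawal counts shift toward SD-809.

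The documents establish the possibility and its direction in Part B. They do not establish that the shift will occur, or how large it will be. The figure of roughly 3 to 14 points rests entirely on the assumed reporting and background rates and on independence; with no reporting it is zero. The consequence is a descriptive safety table that could mislead, and separating the terms is a cheap improvement to it.

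**What to change.** In SAP section 7.2.3, before unblinding, fix a short list of preferred terms that denote worsening of TD. Present Part B adverse-event incidence by arm twice: for all events, and with those terms excluded. Show the TD-worsening terms on their own line.

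Label the second table *AEs other than TD worsening*. It should not be called the tolerability comparison. Placebo patients stop the drug abruptly after at least 4 weeks on a stable dose, so the remaining events may still include other effects of withdrawal; a footnote should say so.

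The change uses data already collected and leaves event collection, clinical management and the efficacy analysis as they are. It costs one more descriptive table and a short coded list.
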